## INTRODUCTION

Extensor tendon injuries of the hand are common due to the superficial anatomical location of the tendons and the relatively thin soft-tissue envelope over the dorsum of the hand and wrist. Injuries involving zones VI to VIII, as defined by Verdan's classification, are particularly prone to postoperative complications, including peritendinous adhesions, extensor lag, stiffness, and delayed return to function. Despite advances in suture techniques and standardized rehabilitation protocols, adhesion-related functional impairment remains a persistent clinical challenge following extensor tendon repair [1,2].

Postoperative adhesions have been reported in up to 30–40% of extensor tendon injuries, even when repairs are performed under optimal conditions and followed by early controlled mobilization [3]. Adhesion formation results from an exaggerated fibroproliferative response within the peritendinous environment, leading to impaired tendon gliding, loss of excursion, and secondary joint stiffness. This pathological process is particularly problematic in zones VI–VIII, where tendons traverse beneath the extensor retinaculum and are closely related to subcutaneous tissues, increasing susceptibility to friction and scarring [4].

Several strategies have been explored to mitigate adhesion formation after tendon repair, including refinement of core suture techniques, epitendinous augmentation, early active motion protocols, and pharmacologic or mechanical anti-adhesion barriers [5,6]. While early mobilization has improved outcomes compared with prolonged immobilization, it has not eliminated adhesion-related morbidity, and aggressive motion may increase the risk of repair site failure in certain clinical scenarios [7].

Biologic barrier membranes have emerged as a promising adjunct to tendon repair, aiming to modulate the local healing environment rather than relying solely on mechanical or rehabilitative strategies. Experimental and clinical studies have demonstrated that biologic wraps, particularly amniotic membrane-based products, can reduce peritendinous fibrosis and improve functional outcomes after extensor tendon repair, especially in zone VI injuries [8–10]. However, limitations related to availability, processing variability, and regulatory considerations have restricted their widespread adoption. Unlike amniotic membrane, HPTC is a standardized, acellular scaffold with defined composition, consistent degradation kinetics, and a well-established safety record across multiple surgical disciplines.

High-purity type I collagen (HPTC) is a bioengineered, acellular collagen matrix composed of more than 97% pure type I collagen, manufactured to preserve the native triple-helical structure while eliminating immunogenic proteins, elastin, and lipids. Type I collagen is the

principal structural component of native tendon extracellular matrix and plays a central role in cellular adhesion, migration, angiogenesis, and tissue remodeling during healing [11,12]. When processed to high purity, collagen matrices demonstrate excellent biocompatibility, predictable biodegradation, and minimal inflammatory response.

HPTC is flexible, translucent, and easily tailored intraoperatively, allowing it to be fashioned as a loose circumferential wrap or sleeve around repaired tendons without increasing bulk or restricting tendon gliding. Preclinical studies have shown that collagen–glycosaminoglycan scaffolds can significantly reduce early postoperative tendon adhesions while preserving tensile strength and intrinsic healing [13,14]. These findings provide a strong biological rationale for the use of HPTC as a peritendinous barrier in tendon repair.

The safety and clinical efficacy of HPTC have been well established across a range of surgical applications. Multiple randomized controlled trials and prospective clinical studies by Narayan and colleagues have demonstrated that HPTC promotes faster healing, improved tissue quality, reduced pain, and favourable scarring outcomes in chronic wounds, pressure ulcers, diabetic foot ulcers, venous leg ulcers, and complex reconstructive settings [15–19]. Importantly, these studies consistently report excellent tolerability and an absence of foreign body reactions, supporting the use of HPTC in sensitive anatomical environments.

Despite this growing body of evidence, the application of HPTC as a biologic wrap around extensor tendon repair sites has not previously been evaluated in a randomized controlled clinical trial. Given the strong biological plausibility of type I collagen scaffolds, the demonstrated benefit of biologic wraps in reducing tendon adhesions, and the reproducible clinical performance of HPTC in other tissue systems, it is logical to investigate whether HPTC wrapping can improve functional outcomes following extensor tendon repair of the hand.

We therefore conducted a multicentric RCT to evaluate the effect of HPTC wrap on total active motion, adhesion-related morbidity, and patient-reported outcomes at eight weeks following extensor tendon repair in zones VI–VIII.

## **MATERIALS AND METHODS**

### **Study Design**

This study was designed as a prospective, multicentric, randomized controlled trial evaluating the effect of high-purity type I collagen (HPTC) wrap applied around extensor tendon repair sites in zones VI–VIII of the hand. The trial employed a parallel-group design with 1:1 allocation to either standard extensor tendon repair with adjunctive HPTC wrap or standard extensor tendon repair alone. The primary purpose of the study was therapeutic, with the objective of improving functional outcomes by reducing adhesion-related morbidity following tendon repair.

The trial was conducted at two tertiary referral centres specializing in plastic, reconstructive, and hand surgery – Adichunchangiri Institute of Medical Sciences, B G Nagara and Mysore Medical College and Research Institute, Mysuru. The trial was prospectively registered with ClinicalTrials.gov (Identifier: NCT07335653; registered 2026-01-13) and approved by the Institutional Ethics Committee (Approval No.: AIMS/IEC/270/2025 on 2025-12-17). The study protocol was approved by the Institutional Ethics Committees of the participating centres, and the trial was conducted in accordance with the Declaration of Helsinki and Good Clinical Practice guidelines. Written informed consent was obtained from all participants prior to enrolment.

This study was conducted and reported in accordance with the CONSORT (Consolidated Standards of Reporting Trials) 2010 guidelines for randomized controlled trials.

### **Study Population**

Adult patients aged 18 to 65 years presenting with acute extensor tendon injuries of the hand involving zones VI, VII, and/or VIII were screened for eligibility. Only patients with complete extensor tendon lacerations involving at least 50% of the tendon cross-sectional area and requiring primary repair were considered for inclusion. Surgical repair was required to be performed within 72 hours of injury.

Patients with crush or avulsion injuries, segmental tendon loss requiring grafting or tendon transfer, associated open fractures requiring dorsal plating across the repair site, prior surgery or significant scarring in the region, major associated nerve injuries requiring grafting, uncontrolled systemic illness, active infection, known hypersensitivity to collagen, pregnancy, or inability to comply with postoperative rehabilitation were excluded.

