### **Randomization, Allocation Concealment, and Blinding**

Eligible patients were randomized in a 1:1 ratio to the experimental or control group using a computer-generated randomization sequence with variable block sizes of four and six. The randomization sequence was prepared by an independent statistician not involved in patient care.

Allocation concealment was ensured using sequentially numbered, opaque, sealed envelopes, which were opened in the operating room after confirmation of eligibility and completion of tendon exposure. Due to the nature of the intervention, blinding of the operating surgeon and patient was not feasible. However, outcome assessors, including hand therapists performing functional measurements and clinicians evaluating outcomes, were blinded to group allocation. The data analyst was also blinded to treatment assignment.

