### **Surgical Technique**

All procedures were performed under regional or general anaesthesia with tourniquet control. The affected upper limb was positioned on a hand table, and standard sterile preparation and draping were performed. A dorsal longitudinal or zig-zag incision was made over the injured extensor tendon, incorporating the traumatic wound where feasible.

The extensor tendon ends were identified, and devitalized tissue was carefully debrided while preserving maximal tendon length. The tendon was mobilized sufficiently to allow tension-free repair, taking care to minimize disruption of surrounding paratenon and soft tissues.

Primary tendon repair was performed using a standardized core suture technique, typically a modified Kessler or four-strand repair, with nonabsorbable monofilament suture material (4-0). The core repair was reinforced with a circumferential running epitendinous suture using fine monofilament suture (6-0) to improve repair strength and smooth the tendon surface.

In the experimental group, following completion of the tendon repair and before skin closure, a sterile HPTC (Surgicoll-Mesh®) sheet was hydrated in normal saline according to manufacturer instructions. The membrane was cut into a rectangular strip measuring approximately 2 to 4 cm in length and 1 to 1.5 cm in width, tailored to the diameter of the repaired tendon. The HPTC strip was wrapped circumferentially around the repair site as a loose sleeve, ensuring overlap of approximately 2 to 3 mm at the edges. The wrap was secured using cyanoacrylate tissue adhesive, applied to the overlapping edges of the collagen membrane and sparingly to the epitenon (Figures 1 & 2). Care was taken to avoid constriction, folding, or bulk that could impede tendon gliding, particularly beneath the

extensor retinaculum in zone VII. Gentle passive flexion and extension were performed intraoperatively to confirm smooth tendon excursion and absence of mechanical block. In the control group, no biologic wrap or anti-adhesive adjunct was applied after tendon repair. Skin closure, dressing, and splinting were identical in both groups.

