## **Statistical Analysis Plan**

All analyses were performed using an intention-to-treat approach, including all randomized participants in their allocated groups. A per-protocol analysis will be conducted as a secondary exploratory analysis.

Continuous variables were expressed as mean  $\pm$  standard deviation or median with interquartile range, depending on distribution. Categorical variables will be expressed as frequencies and percentages. Between-group comparisons of the primary outcome were performed using an independent samples t-test for normally distributed data or the Mann–Whitney U test for non-normally distributed data. Proportions of patients achieving good or excellent functional outcomes based on established extensor tendon scoring systems were compared using chi-square or Fisher’s exact tests.

Secondary outcomes were analysed using appropriate parametric or non-parametric tests. Repeated-measures analysis of variance or mixed-effects models was used to evaluate changes in functional scores over time. Effect sizes were reported using Cohen’s d for continuous outcomes and relative risk or odds ratios for categorical outcomes, with corresponding 95% confidence intervals. Two-sided p-values less than 0.05 was considered statistically significant.

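### The hypersensitivity exclusion names collagen only, although the experimental procedure also introduces a cyanoacrylate adhesive

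*Combined protocol and SAP*

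**What the plan says.** The exclusion list in Study Population ends with "known hypersensitivity to collagen, pregnancy, or inability to comply with postoperative rehabilitation were excluded". The only allergy it names is "known hypersensitivity to collagen", and the list has no general wording about study materials or components.

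Surgical Technique describes how the wrap is fixed: "The wrap was secured using cyanoacrylate tissue adhesive, applied to the overlapping edges of the collagen membrane and sparingly to the epitenon". This belongs to the sequence that begins "In the experimental group, following completion of the tendon repair and before skin closure". No alternative fixation is given, and nothing is said about a patient who cannot receive the adhesive. For the comparator the same section states: "In the control group, no biologic wrap or anti-adhesive adjunct was applied after tendon repair". It adds: "Skin closure, dressing, and splinting were identical in both groups". The closure material is not named.

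Under Randomization, Allocation Concealment, and Blinding, the envelope is "opened in the operating room after confirmation of eligibility and completion of tendon exposure". The Statistical Analysis Plan specifies intention-to-treat, "including all randomized participants in their allocated groups", with a per-protocol analysis as secondary and exploratory.

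**The concern.** By excluding collagen hypersensitivity, the plan accepts that a known reaction to a material left at the repair site is a reason not to enrol. It applies that principle to one of the two materials the experimental arm receives.

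A patient who has reacted to cyanoacrylate before, for example at an earlier wound closure, passes every written criterion. If the envelope then assigns the wrap, the surgeon must either use the adhesive or depart from the described technique. The first is an avoidable exposure. The second is a departure that, at tendon level, can occur in one arm only. Such a patient would stay in the intention-to-treat comparison with a weakened or absent treatment, and might drop out of the per-protocol set from the experimental side alone.

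**Working it through.** **Step 1. Compare the sections.**

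| Item | Experimental arm | Control arm | Covered by the hypersensitivity criterion? |
|---|---|---|---|
| Collagen sheet | Yes | No | Yes |
| Cyanoacrylate at tendon level | Yes | No | No |
| Skin-closure material | Same in both arms, not stated | Same in both arms, not stated | Cannot be judged |

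Of the other exclusions, the nearest is uncontrolled systemic illness, which does not reasonably cover a contact or material allergy. Eligibility is confirmed before the envelope is opened, so the listed criteria are the last check the protocol defines before allocation. The gap is therefore in the text and does not depend on any calculation.

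**Step 2. Reproduce the planned sample size.** Inputs from Sample Size Calculation: standardized effect d = 0.75, two-sided alpha 0.05, power 80%, 1:1 allocation.

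n per group = 2 × [(1.960 + 0.842) / 0.75]² = 27.91, rounded up to 28.

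This matches the stated 28. The t-test version gives 28.90, so 29. The plan then enrols 30 per group. An added exclusion does not enter this formula, so the planned number does not change.

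**Step 3. How likely is such a patient in the experimental arm?** The documents give no prevalence p of known cyanoacrylate reaction, so p is an assumption. The chance of at least one among 30 is 1 − (1 − p)^30, and the expected number is 30p.

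| Assumed p | Chance of at least one in 30 | Expected number |
|---|---|---|
| 0.1% | 3.0% | 0.03 |
| 0.5% | 14.0% | 0.15 |
| 1% | 26.0% | 0.30 |
| 2% | 45.5% | 0.60 |

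The count is restricted to the 30 experimental patients, because only they undergo the adhesive step at tendon level.

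**Step 4. What would a withheld wrap cost statistically?** Suppose k of the 30 experimental patients do not get the wrap and gain nothing from their allocation, all 30 per arm are analysed, and the standard deviation is unchanged. The diluted effect is 0.75 × (1 − k/30). Power by the normal approximation is Φ(d × √(30/2) − 1.960).

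| k | Diluted d | d × √15 | Power, normal | Power, t-test |
|---|---|---|---|---|
| 0 | 0.750 | 2.905 | 82.8% | 81.5% |
| 1 | 0.725 | 2.808 | 80.2% | 78.8% |
| 2 | 0.700 | 2.711 | 77.4% | 76.0% |

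The first withheld wrap costs 82.8 − 80.2 = 2.6 points. At the top of the assumed range, the expected loss is roughly 0.6 × 2.6 = 1.6 points if every such patient has the wrap withheld. At the bottom it is 0.03 × 2.6 = 0.08 points.

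**The case against.** The strongest reply is that this is an omission with little practical effect. Four parts of it deserve an answer.

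- **Sites are not forced to enrol.** A reader might infer that a site must take such a patient and that the problem can appear only after the envelope is opened. The documents do not support that. An exclusion list does not compel enrolment, the trial states that it follows Good Clinical Practice, and a known reaction is by definition knowable before surgery. This stands. What remains is that the protocol does not direct anyone to ask. An unwritten exclusion may be applied differently by surgeons at the two centres, or not at all.
- **The frequency is unsupported.** This also stands: the 0.1% to 2% range is an assumption. It would be wrong to quote a probability over all 60 patients as the size of this problem, since control patients do not undergo the adhesive step.
- **The damage to the analysis is negligible.** Largely correct. The per-protocol set is exploratory and its adherence rules are not defined, and Study Design describes the experimental treatment as repair plus the collagen wrap, without naming the adhesive. So it is not established that a different fixation would make a patient non-adherent.
- **One-sidedness is not fully proven.** Closure is the same in both arms, but its material is not stated, so cyanoacrylate exposure at the skin in both arms cannot be ruled out. Only the tendon-level step is shown to be confined to the experimental arm. The quantity placed on the epitenon is also described as sparing.

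None of this removes the gap between the eligibility list and the procedure.

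**Conclusion.** The point holds as a gap in eligibility. The written criteria admit a patient with a known reaction to one of the two materials that the experimental arm receives, and the plan does not say what happens if that patient is allocated to the wrap.

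Its importance is mainly participant safety. The chance that it arises in the experimental arm is about 3% to 45%, entirely conditional on the assumed prevalence of 0.1% to 2%. The statistical effect is about 2.6 points of power per withheld wrap, and that figure itself assumes such a patient gets no benefit.

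A reader might go further and infer that the primary comparison of total active motion is biased or its validity threatened. The documents do not support that: fewer than one such patient is expected even at 2%, and the sample size calculation is unaffected. It is worth correcting because the correction is cheap.

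**What to change.** The sponsor should reconcile Study Population with Surgical Technique so that the hypersensitivity criterion covers every material the experimental procedure introduces, that is, the collagen and the adhesive. The check should be made in every patient when eligibility is confirmed, before the envelope is opened. That keeps it independent of allocation and leaves the randomized comparison intact. Stating the skin-closure material would also show whether both arms are exposed.

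The cost is a few words in the criteria, one screening question and an occasional extra screen failure. The sample size does not change. Much of the document is written in the past tense, so the change can apply only to patients still to be enrolled.

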### **Randomization, Allocation Concealment, and Blinding**

Eligible patients were randomized in a 1:1 ratio to the experimental or control group using a computer-generated randomization sequence with variable block sizes of four and six. The randomization sequence was prepared by an independent statistician not involved in patient care.

Allocation concealment was ensured using sequentially numbered, opaque, sealed envelopes, which were opened in the operating room after confirmation of eligibility and completion of tendon exposure. Due to the nature of the intervention, blinding of the operating surgeon and patient was not feasible. However, outcome assessors, including hand therapists performing functional measurements and clinicians evaluating outcomes, were blinded to group allocation. The data analyst was also blinded to treatment assignment.

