### **Postoperative Splinting and Rehabilitation Protocol**

All patients were placed in a standardized dorsal protective splint with the wrist in extension and the metacarpophalangeal joints positioned according to the involved zone and institutional extensor tendon protocol. Postoperative rehabilitation was standardized across both groups and supervised by certified hand therapists.

Initial immobilization was maintained for five to seven days. Controlled early active or early controlled motion protocols were then initiated based on institutional standards for zones VI–VIII, progressing to increased range of motion exercises by three to four weeks and gradual strengthening by six weeks. No additional anti-adhesion agents or topical products targeting tendon healing were permitted during the study period.

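### Two centres with institution-specific splinting and motion programmes: allocation by centre is undocumented and the primary test has no centre term, so chance centre imbalance goes uncorrected and some precision is lost

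*Combined protocol and SAP*

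**What the plan says.** Study Design: "The trial was conducted at two tertiary referral centres", with parallel groups.

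Randomization, Allocation Concealment, and Blinding: allocation is 1:1, and was made "using a computer-generated randomization sequence with variable block sizes of four and six". The list is again referred to in the singular: "The randomization sequence was prepared by an independent statistician not involved in patient care". Concealment used "sequentially numbered, opaque, sealed envelopes, which were opened in the operating room". No stratification factor is named, and nothing says how the envelopes were shared between the two hospitals.

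Postoperative Splinting and Rehabilitation Protocol: "Postoperative rehabilitation was standardized across both groups and supervised by certified hand therapists". In the same section, the metacarpophalangeal joints are "positioned according to the involved zone and institutional extensor tendon protocol", and "Controlled early active or early controlled motion protocols were then initiated based on institutional standards for zones VI–VIII". The section does not say whether the two institutions' standards are the same.

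Statistical Analysis Plan: the primary outcome is compared by an independent-samples t-test, or by a Mann–Whitney test if the data are not normal. Mixed models are mentioned only for functional scores over time. Centre appears nowhere as a covariate, stratum or random effect.

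**The concern.** The Introduction treats early mobilisation as something that changes outcome after tendon repair. If the two hospitals splint or mobilise differently, mean TAM at eight weeks may differ between them for reasons unrelated to the wrap. With 60 patients, a single list shared by two centres can by chance put noticeably more of one centre's patients in one arm. An unadjusted comparison then carries part of the centre difference in the reported treatment effect. It also leaves the between-centre variance in the error term, where a centre term would remove it.

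If allocation was in fact balanced within centre, there is no imbalance to correct, but the analysis still ignores the balance and its standard error is too large. In either case the primary test is not the best one for the design, and the reader cannot tell which case applies.

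**Working it through.** **Inputs from the documents.** Two centres (Study Design); 1:1 allocation with blocks of four and six (Randomization section); effect size 0.75, two-sided alpha 0.05, power 80%, at least 28 per group, 30 per group planned (Sample Size Calculation).

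**Assumed, because the documents do not give them.** The enrolment split between centres, and the centre difference in TAM, c, in SD units. Both are shown as ranges.

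**1. The plan's own figure.** n = 2(1.960 + 0.842)² / 0.75² = 27.9, so 28 per group, as stated. The exact t calculation gives 28.9, so 29. At 30 per group the exact power is 81.5%, which is the reference below.

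**2. Chance imbalance if both centres draw from one list in arrival order.** Let one centre enrol 20 of 60, and let X be the number of those 20 in the wrap arm. Ignoring blocks, X is hypergeometric (60, 30, 20), and P(X ≤ 7 or X ≥ 13) = 2 × 0.085 = 0.170. Simulating blocks of four and six with random interleaving gives about 0.17 as well, so overall blocking does not protect centre balance in this case. The same three-patient deviation has probability 10%, 16% or 20% if the centre enrols 12, 18 or 30 of 60.

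**3. Effect of a 13:7 split on the estimate.** Shift = c × (13/30 − 7/30) = 0.2c.

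| Assumed c (SD) | Shift (SD) | Share of 0.75 |
|---|---|---|
| 0.25 | 0.05 | 7% |
| 0.5 | 0.10 | 13% |
| 0.8 | 0.16 | 21% |

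**4. If each centre received a consecutive run of envelopes.** All blocks have even length, so a run of 20 starting at a block boundary ends after complete blocks or part-way through one, with two or four places of it used. The excess of one arm over the other is then at most two, that is 11:9. A simulation of 40,000 lists agrees: no split went beyond 11:9.

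**5. Long-run behaviour of the planned test.** This was simulated with N = 60, total SD fixed at 1, 8,000 runs per scenario, c of 0.25, 0.5 and 1.0, and centre splits of 50:50 and 70:30.
- One unstratified list, unadjusted t-test: type I error 0.049 to 0.054, and the mean estimate equals the true effect.
- Allocation stratified by centre, unadjusted t-test: type I error 0.047 (50:50) and 0.041 (70:30) at c = 0.5, and 0.022 and 0.029 at c = 1.0. The test is conservative.

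**6. What a centre term gains.** With total SD 1 and equal centres, the residual variance after adjustment is 1 − 0.25c². The effect relative to the residual SD becomes 0.75 / √(1 − 0.25c²), tested on 57 degrees of freedom.

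| Assumed c (SD) | Residual variance | Power with centre term | Power as planned |
|---|---|---|---|
| 0.25 | 0.984 | 82% | 81.5% |
| 0.5 | 0.938 | 84% | 81.5% |
| 0.8 | 0.840 | 88% | 81.5% |
| 1.0 | 0.750 | 91% | 81.5% |

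The formula assumes centres balanced between arms. In simulation with one unstratified list and a centre term, power was 81%, 84% and 91% at c = 0.25, 0.5 and 1.0 for equal centres (81%, 82% and 89% at 70:30), against 81–82% unadjusted. Adjustment without stratification therefore recovers most of the gain.

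**The case against.** The strongest reply is that nothing here makes the trial invalid. Randomisation makes the unadjusted estimate unbiased, and the t-test already allows for chance imbalance; step 5 confirms both. The documents give no centre difference, and both hospitals share the broad rehabilitation timetable. If the effect size of 0.75 is scaled by the total SD, between-centre variance is already in the calculation and no planned power is lost. All of this stands, and it limits the point to conditional imbalance and precision.

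Three stronger readings are tempting, and the documents support none of them.

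- A reader might infer that blocking balances neither centre, because numbered paper envelopes from one list cannot be drawn in order at two sites. If so, the envelopes must have been divided somehow, and consecutive batches would keep each centre close to balance (step 4). The 17% applies only if the centres interleave on one list. That there was one unstratified list is itself inferred from a singular noun and from silence.
- A reader might infer that the unblinded surgeon chooses the motion programme once the arm is known. No section says so. Motion follows institutional standards under hand therapists, and the Surgical Technique section states that splinting did not differ between arms.
- A reader might infer that the rehabilitation section contradicts itself. It does not: the statement of standardisation refers to the two arms, and the institutional standards refer to centres and zones. Both can be true.

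**Conclusion.** The point holds as one of efficiency and documentation. The plan has two centres that may treat differently, no described allocation by centre, and a primary test that ignores centre. Any imbalance that occurs stays in the reported estimate. Under the interleaved-list assumption with 20 of 60 patients at one centre, a 13:7 or worse split has a 17% chance, and a 13:7 split moves the estimate by 7% to 21% of the planned effect for centre effects of 0.25 to 0.8 SD. If the envelopes went out in consecutive batches, that risk largely disappears and the cost is a conservative test instead.

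The power given up is negligible at a centre effect of 0.25 SD, about 1 to 2 points at 0.5 SD and about 9 points at 1.0 SD. The point matters in practice only if the centres differ by about 0.5 SD or more, which the documents neither establish nor rule out. There is no systematic bias and no type I error inflation.

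**What to change.** **Statistical Analysis Plan.** Make the primary analysis a linear model of eight-week TAM on arm and centre, reporting the adjusted difference with its 95% confidence interval. If a non-parametric test is needed, replace the Mann–Whitney test by a van Elteren test stratified by centre. This is appropriate however the envelopes were divided.

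**Randomization section.** If enrolment has not begun, use a separate blocked sequence and envelope set for each centre, and say so. If it has begun, leave the allocation alone, state whether the sequence was stratified and how the envelopes were divided between the hospitals, and report allocation by centre and arm.

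**Cost.** One model degree of freedom and, if still possible, a second list and envelope set. No extra patients.

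### The allocation envelope may be opened once the tendon is exposed, so an unblinded surgeon can do the repair knowing the arm, although the arms differ only after the repair

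*Combined protocol and SAP*

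**What the plan says.** The section Randomization, Allocation Concealment, and Blinding describes sequentially numbered, opaque, sealed envelopes, "which were opened in the operating room after confirmation of eligibility and completion of tendon exposure". It adds that "blinding of the operating surgeon and patient was not feasible", while outcome assessors and the data analyst are blinded.

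Surgical Technique then gives one sequence for all patients: incision, identification and debridement of the tendon ends, mobilization, core suture, epitendinous suture. Two steps leave room for judgement:

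- Core suture: "Primary tendon repair was performed using a standardized core suture technique, typically a modified Kessler or four-strand repair". No rule for choosing between the two is given.
- Mobilization: "The tendon was mobilized sufficiently to allow tension-free repair, taking care to minimize disruption of surrounding paratenon and soft tissues".

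The arms part only afterwards. In the experimental arm, "following completion of the tendon repair and before skin closure, a sterile HPTC (Surgicoll-Mesh®) sheet was hydrated in normal saline". For the other arm: "In the control group, no biologic wrap or anti-adhesive adjunct was applied after tendon repair". The section then says that closure, dressing and splinting did not differ between groups. It makes no such statement about the repair.

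**The concern.** A surgeon who knows the arm while repairing the tendon can, without intending to, choose a different core suture, mobilize more or less, or suture with more or less care. The Introduction itself lists core suture technique and epitendinous augmentation among the strategies for reducing adhesions, so these steps plausibly affect the primary outcome, total active motion at eight weeks. A difference in repair between arms would then be counted as an effect of the wrap. Blinded assessors would measure that difference accurately, but they could not separate it from the wrap's effect. The Statistical Analysis Plan compares the arms without adjusting for repair technique.

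The reason given for not blinding the surgeon is the nature of the intervention. That reason applies from the wrap step onward and does not explain why the arm should be known during suturing.

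A second, smaller issue concerns eligibility. Segmental loss needing a graft or transfer is an exclusion under Study Population. If it becomes evident only on debridement, and the envelope is already open, the patient has been randomized.

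**Working it through.** **1. Order of events.** Setting the two sections side by side:

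| Step | Arm may be known? | Planned difference between arms? |
|---|---|---|
| Eligibility confirmed, tendon exposed | No | No |
| Debridement, mobilization | Possibly (depends on what exposure covers) | No |
| Core suture, epitendinous suture | Yes | No |
| Wrap applied, or not | Yes | Yes |
| Closure, dressing, splint | Yes | No, stated to be identical |

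The suturing row is the problem: the arm may be known there, the surgeon has some discretion, and nothing in the treatment contrast requires that knowledge.

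**2. The plan's own sample size.** Inputs from Sample Size Calculation: effect size 0.75, two-sided alpha 0.05, power 80%, 1:1 allocation.

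- Normal approximation: n per arm = 2 × ((1.960 + 0.842) / 0.75)² = 27.9, so 28. The plan's figure is reproduced.
- Exact t-test: 28.9, so 29 per arm. Power is 78.7% at 28 and 81.5% at the planned 30.

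Moving the envelope opening changes none of these numbers.

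**3. What a bias could do (illustration only).** The documents give no figure for such a bias. Assume that knowing the arm shifts the share of one repair type by 20 to 30 percentage points, and that the two types differ by 0.5 SD in total active motion. The spurious difference is then

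- 0.20 × 0.5 = 0.10 SD, up to 0.30 × 0.5 = 0.15 SD.

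For a two-sample t-test with 30 per arm (58 degrees of freedom), the noncentrality is d × √(30/2):

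| Spurious d | Noncentrality | Two-sided rejection rate, no true effect |
|---|---|---|
| 0 | 0 | 5.0% |
| 0.10 | 0.387 | 6.7% |
| 0.15 | 0.581 | 8.8% |
| 0.20 | 0.775 | 11.9% |

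The last row lies outside the assumed range: at 0.5 SD between techniques it would need a 40-point shift (0.40 × 0.5 = 0.20).

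**4. The opposite direction.** If unwrapped controls received the more careful repair, the same 0.10 to 0.15 SD would be subtracted from a true effect. A true 0.75 would appear as 0.65 to 0.60, and exact power at 30 per arm would fall from 81.5% to 69.7% or 62.8%. The documents give no basis for preferring either direction.

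**The case against.** The case on the other side is substantial.

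- **Timing.** The text sets an earliest time for opening and does not say that the envelope was opened before the repair. Exposure is not defined as a step, so debridement and mobilization may belong to it. This stands, and limits the claim to what the plan permits. The natural reading still leaves the suturing after the opening.
- **Standardization.** The core technique is called standardized, suture calibres are fixed and an epitendinous suture is part of every repair. This narrows the room for a difference but does not close it, because the core suture is "typically a modified Kessler or four-strand repair" and the extent of mobilization is a matter of judgement.
- **Concealment.** A reader might infer that allocation concealment failed. It did not: eligibility is confirmed before opening, so concealment at enrolment is intact.
- **Intention to treat.** A reader might infer that patients found unsuitable during the repair would be dropped, breaking the intention-to-treat set and using up the two-patient margin between 28 and 30 per arm. The documents do not support this. The Statistical Analysis Plan keeps every randomized participant in the allocated group, and no text allows removal. Such a discovery would also be an exception, since eligibility should already have been confirmed. Inability to achieve a tension-free repair is not an exclusion at all; it appears only as a surgical aim.
- **Size.** Every bias figure above rests on assumptions with no source in the documents. This stands in full.

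**Conclusion.** The plan permits an unblinded surgeon to know the arm while doing the repair, although the treatments differ only once the repair is complete. That is an avoidable risk of performance bias, and blinding of assessors and analyst does not address it. It is a worthwhile, inexpensive improvement; it does not by itself invalidate the trial.

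The size and direction of any bias are unknown. Under the stated assumptions (a 20 to 30 point shift in technique and 0.5 SD between techniques), the false-positive rate would rise from 5% to between 6.7% and 8.8%. A shift favouring controls would instead hide part of a true effect. A reader might take these figures as the trial's actual error rate, or conclude that repairs did differ by arm. Neither follows, since the documents contain no evidence of a difference.

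**What to change.** **If operations remain to be done.** Amend the envelope sentence in Randomization, Allocation Concealment, and Blinding so that the envelope is opened only after the core and epitendinous sutures are complete and eligibility has been reconfirmed, immediately before the step at which the tendon is either wrapped or closed over. Record the opening time and the core technique on the case report form. A patient found to have segmental loss during debridement then becomes a screen failure. Under the present sequence that patient could already be randomized and would stay in the intention-to-treat set.

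**If operations are already done.** Much of the text is in the past tense, so this may be the case. Report when envelopes were actually opened and tabulate repair technique by arm where it was recorded; the documents do not show that it was. Any analysis adjusted for technique should be labelled a sensitivity analysis on a post-randomization variable, because technique may itself have been influenced by knowledge of the arm.

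**Cost.** One sentence in the protocol, one or two fields on the case report form and a minor change to operating-room workflow. Preparation of the sheet is already placed after the repair. No extra patients are needed.
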